Prazosin should not be taken concurrently with trazodone. Potential participants who are taking trazodone for sleep and who are willing to discontinue will be washed out before starting this study. Care should be taken when alpha-1 blockers are combined with erectile dysfunction medications. We will be following VA pharmacy prescribing guidelines regarding these medications. They will not be allowed during the Titration Period. Once the Stable Dose Period has been reached, erectile dysfunction medications will be allowed at 1/2 the usual clinical dose.

In our current study of prazosin in active duty SMs at Madigan, we have noticed an increased use of dietary supplements containing nitrates. In one case, a participant experienced three episodes of priapism while taking one of these supplements with prazosin. Therefore, use of these supplements and supplements containing stimulants (such as ephedra) will be exclusionary for the duration of the study. Participants who take these supplements will be asked to discontinue them before the Preliminary Screening Period begins.

In post-marketing experience, intraoperative floppy iris syndrome (IFIS) has been observed during cataract surgery in some patients who are taking or have taken alpha-1 blockers. The patient's ophthalmologist should be prepared for possible modifications to the surgical technique to reduce the surgical risk of IFIS. If a patient needs to have cataract surgery, he/she should tell his/her eye surgeon that he/she may have taken prazosin in a research study.

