**Risk Management and Emergency Response:** Evaluation for adverse effects and review of concurrent medications will be completed at all study visits. Participants are asked about suicidal ideation at each in-person visit. If endorsed, participants will be assessed as to their level of risk and the level of care required to keep them or others from harm. If a participant requires inpatient treatment in order to prevent harm or is found to have symptoms of disorganized thought processes secondary to psychosis, mental health personnel will be notified immediately to assist with appropriate triage and referral. Vital signs, including orthostatic blood pressure (BP) and heart rate (HR) will be performed at all study visits. Systolic and diastolic BP and HR will be obtained following 10 minutes of rest, and repeated following 2 minutes of standing. Occurrences of lightheadedness, dizziness on standing, palpitations, drowsiness, nausea, nasal congestion, peripheral edema, worsening of HA, and other adverse effects will be rated by the clinician. For vital signs parameters, unacceptable side effects will include resting hypotension (systolic BP<100 mm Hg) and clinically meaningful hypotension (20 mm Hg or more drop in systolic BP accompanied by dizziness, lightheadedness, or syncope).

For participants taking other antihypertensive medications, their primary care provider will be informed of clinically significant BP reductions at any time during the study, to allow adjustment of the participant's antihypertensive regimen. As a further precaution, male subjects will be advised to sit on the toilet for urination the first two nights to avoid orthostatic hypotension secondary to micturition syncope.

Safety monitoring is based on long-term clinical experience with prazosin. Prazosin was first introduced in 1976 under the trade name Minipress (Pfizer) for clinical management of hypertension, and later became widely prescribed for urinary outflow obstruction secondary to benign prostatic hypertrophy. It has been safely prescribed to large numbers of middle-aged and older people over the past 40 years. The following information regarding the side effect profile and safety record of prazosin is a synopsis from the Minipress package insert: "The most important adverse effect to be considered when prescribing

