prazosin is a "first dose effect" manifested by syncope with sudden loss of consciousness believed to be due to postural hypotension in approximately 1% of patients given an initial dose of 2 mg or greater. This rare adverse effect is self-limiting and in most cases does not recur after the initial period of therapy or during subsequent dose titration. However, patients should always be started on 1 mg of prazosin. In clinical trials of prazosin, most frequent adverse reactions were dizziness (10%), HAs (8%), drowsiness (8%), lack of energy (7%), weakness (7%), palpitations (5%), and nausea (5%). Less frequent adverse reactions (1-4%) were: vomiting, diarrhea, constipation, edema, orthostatic hypotension, dyspnea, syncope, vertigo, depression, nervousness, rash, urinary frequency, and nasal congestion. Fewer than 1% of patients have reported the following (causal reactions sometimes not established): abdominal discomfort or pain, tachycardia, paresthesias, hallucinations, pruritus, incontinence, impotence, and priapism..."

Through extensive experience of our group, including open-label clinical studies, placebo-controlled trials, and clinical application, prazosin has demonstrated a favorable safety profile. Several thousand active-duty SMs and Veterans with PTSD have now been treated with prazosin at VA Puget Sound and Madigan, as well as at other centers, including the Spokane, Portland, and Cleveland VA Medical Centers. It has been estimated that over 70,000 Veterans nationwide are being treated with prazosin for PTSD. Approximately 5% of those treated with prazosin have discontinued it secondary to subjectively unpleasant side effects, most commonly transient orthostatic dizziness, nasal congestion, or exercise-induced tachycardia.

Regarding other participant safety issues, procedures relevant to the war-zone trauma and TBI population include exclusion of participants with severe psychiatric instability or severe situational life crises, including evidence of being actively suicidal or homicidal, or any behavior that poses an immediate danger to the participant or others. A female Rater will be available to perform interview-based assessments, if requested by female participants. Trained personnel will be on call at all times to receive calls from participants regarding any adverse events; participants will be provided with 24-hour emergency contact numbers.

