### 6.0 Reporting

Adverse event reporting will begin after the dispensing of the first dose of study drug.

**Serious adverse events (SAEs):** SAEs (defined as any untoward medical occurrence which may be related to study participation at any time during the study that results in subject death, is life threatening, requires hospitalization, or results in persistent or significant disability/incapacity), will be reported to the PI, or if not available, another clinician investigator immediately upon discovery. SAEs will be reported to the Madigan IRB and DCI per current Madigan policies. The Madigan research monitor and the DSMB will be notified of the submission. A copy of the report will also be sent to the VA Puget Sound IRB per VA guidelines.

**Adverse Events (AEs):** Unexpected, but not serious, AEs, which the PI determines are related or possibly related to research participation, will be reported to each IRB per local guidelines. The Madigan research monitor and the DSMB will be informed of the event. Expected adverse events, which are not serious and possibly related to research participation, will be reported to the Madigan and VA Puget Sound IRBs on the annual report.

**Unanticipated problems:** Involving breach of confidentiality or HIPAA violation or any other risk to the health or welfare of participants that the PI determines are related or possibly related will be reported to each IRB per local guidelines. The Madigan research monitor and the DSMB will be informed of the event.

All other adverse events or problems that the PI determines are unrelated to research participation will be reported to the Madigan IRB/DCI with the annual report.

A summary of all above reports will be sent to the Madigan and VA Puget Sound IRBs with the annual report. Departures from the protocol, which do not involve risks to volunteers or affect the scientific integrity of the study, will be reported annually to the Madigan and VA Puget Sound IRBs. Deviations, which involve unanticipated problems involving risks to volunteers or others, will be reported promptly, using the procedures described in reporting of adverse events above.

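### Section 6.0 allows priapism or syncope treated without admission to be classed as expected and non-serious, and so to reach the IRBs only on the annual report

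*Combined protocol and SAP*

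**What the plan says.** **Seriousness.** Section 6.0 counts an event as serious if it "results in subject death, is life threatening, requires hospitalization, or results in persistent or significant disability/incapacity". No criterion covers an event that is medically important but meets none of these.

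**Routing.** In the same section, SAEs, unexpected related AEs and unanticipated problems each carry a statement that the research monitor and DSMB will be told. For the remaining related events it says only that "Expected adverse events, which are not serious and possibly related to research participation, will be reported to the Madigan and VA Puget Sound IRBs"; the vehicle is the annual report. The term *expected* is not defined and no reference list is named.

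**Priapism and syncope as known hazards.** Under Risk Management and Emergency Response, section 5.1 quotes the package insert. Syncope is among reactions in 1-4% of patients; those below 1% include "hallucinations, pruritus, incontinence, impotence, and priapism". Under Foreseeable Risks it reports, from the group's prazosin study in active-duty SMs at Madigan: "In one case, a participant experienced three episodes of priapism while taking one of these supplements with prazosin". The response is that "use of these supplements and supplements containing stimulants (such as ephedra) will be exclusionary for the duration of the study". Section 5.4 gives priapism as the reason for caution in combining prazosin with trazodone, and requires a washout.

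**What is rated.** Section 5.1 states that "lightheadedness, dizziness on standing, palpitations, drowsiness, nausea, nasal congestion, peripheral edema, worsening of HA, and other adverse effects will be rated by the clinician". Elsewhere in that paragraph syncope appears only as one of the symptoms that make a systolic drop clinically meaningful.

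**The concern.** The protocol takes priapism seriously enough to bar a class of supplements and wash out a drug, and it describes syncope at length as a first-dose risk. The reporting section does not carry that through. Either event can need acute treatment and still end without admission, and the definitions then let it be handled like nasal congestion.

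At stake is how soon oversight bodies hear of it. The research monitor can stop the study or remove a participant, and the DSMB recommends for or against continuation. Both depend on events reaching them while action is still useful. Because *expected* is left open, the two sites could also route the same event differently.

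**Working it through.** There is no stated figure to reproduce, so the check is mainly a walk through the text, followed by two pieces of arithmetic.

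**1. One event through section 6.0.** Take an episode of priapism or syncope treated in an emergency department and sent home, with no threat to life and no lasting disability.
- Serious? None of the four criteria is met.
- Expected? The package-insert text in section 5.1 lists both, so an investigator may say yes. The side-effect list under Foreseeable Risks includes syncope but not priapism, so for priapism an investigator could also say no. Nothing says which list governs.
- If expected and possibly related: IRBs, annual report, and no stated notice to the monitor or DSMB.
- If unexpected and related: each IRB under local guidelines, with monitor and DSMB informed.

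The same clinical event can therefore take a slow or a faster route, depending on an undefined word.

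**2. When the DSMB would see it.** Section 5.1 sets DSMB meetings after 40, 80, 120 and 160 participants have completed. Section 5.7 defines completion as the full 12 weeks at steady dose.
- Randomisation rate: 4-5 per month (section 5.1). Dropout: 30% (section 5.6).
- Completers per month of recruitment: 4 × 0.70 = 2.8 to 5 × 0.70 = 3.5.
- Recruitment needed for 40 completers: 40 / 3.5 = 11.4 to 40 / 2.8 = 14.3 months.
- Time on study: 5-7 weeks' titration plus 12 weeks = 17-19 weeks, or 3.9-4.4 months.
- First meeting: 11.4 + 3.9 = 15.3 to 14.3 + 4.4 = 18.7 months after the first randomisation.
- By then about 75 people are randomised (4 × 18.7), about 50 of them on prazosin (75 × 2/3).
- If completion were read to include dropouts: 40/5 + 3.9 = 11.9 to 40/4 + 4.4 = 14.4 months.
- Expected completers overall: 160 × 0.70 = 112, so on the section 5.7 definition the triggers at 120 and 160 would not be reached.

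**3. How many events.**
- Prazosin arm: 160 × 2/3 = about 107.
- Syncope at 1-4%: 1.1 to 4.3 events.
- Priapism below 1%: fewer than about 1.1 cases. The chance of at least one, 1 − (1 − p)^107, is 10% at p = 0.1%, 42% at 0.5% and 66% at 1%. These values of p are assumptions; the protocol gives only an upper bound.

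These counts are on the high side for the gap itself. They include admitted cases, which are already SAEs. The priapism figure uses both sexes as denominator. Section 5.1 also says that starting at 1 mg and titrating slowly, as here, reduces syncope.

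**The case against.** Much can be said for the plan as written.

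- **The three priapism episodes.** A reader might take them as evidence of what prazosin will do in this trial. The text does not support that. They occurred in one participant of another study by the group, who was taking a nitrate-containing supplement that is prohibited here. They show a recognised hazard and give no rate. A true repeat would also involve a prohibited supplement and so be a protocol departure. Section 6.0 does not leave departures that put volunteers at risk to the annual report, and those amounting to unanticipated problems are reported promptly.
- **Capture.** A reader might infer that priapism would not be recorded. The rated list ends with other adverse effects, adverse events are reviewed at every scheduled contact after drug start, and there is a 24-hour contact number. An episode that is mentioned would be recorded. What is missing is a named prompt. That participants may not volunteer priapism is a reasonable judgement, not something the documents show, and the side-effect form itself is not among them.
- **Notice.** A reader might infer that oversight bodies hear nothing unless the person is admitted. That goes too far. Threat to life and lasting disability also make an event serious. The monitor is charged with keeping up with adverse events of all kinds, the DSMB reviews safety at each meeting and can ask for more data, and the two study teams share expected events under section 8.0. The PI may also choose a faster category. Local IRB policies, which the documents do not reproduce, may be broader.

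These points narrow the concern without removing it. Section 6.0 gives the monitor no stated feed of expected events, section 8.0 shares them between study teams and not with oversight bodies, the first DSMB meeting is late, and discretion over an undefined term is not a safeguard.

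**Conclusion.** The point holds as a gap in reporting definitions. Section 6.0 permits priapism or syncope treated without admission, threat to life or lasting disability to be classed as expected and non-serious. On that classification it reaches the IRBs once a year, with no stated prompt notice to the research monitor or DSMB, and the DSMB could first see it more than a year into the trial. The documents do not show that such an event must take this route or would go unrecorded; the supportable claim is possible delay.

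The size is small in counts: about 1 to 4 syncope events and at most about one priapism case on prazosin. This assumes that the label rates apply, that 160 are randomised 2:1, and, for the meeting times, that recruitment runs at 4-5 per month with 30% dropout. The efficacy analysis is unaffected. The change is worth making because these are the acute harms the protocol itself singles out, and the correction is cheap.

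**What to change.** In section 6.0:
- add a criterion for medically important events to the SAE definition;
- state which reference list decides whether an event is expected, and reconcile the Foreseeable Risks list in section 5.1, which omits priapism, with the package-insert list, which includes it;
- name priapism and syncope for prompt notice to both IRBs, the research monitor and the DSMB, whether or not they are expected or lead to admission.

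In section 5.1, under Risk Management and Emergency Response, add priapism (male participants) and syncope as named items in the list rated by the clinician.

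The cost is a few lines of protocol text, two items on the side-effect form and a handful of extra prompt reports. The change concerns recording and reporting only; dosing and clinical care are untouched.

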# 7.0 Privacy and Confidentiality

The study will both use and disclose PHI. Information to be used are participant name, telephone numbers, address, medical record number (DOD ID number), SSN (for creating or updating a medical record at VA Puget Sound and for purposes of remuneration, and all elements of dates (i.e. birthdate, dates of admission, discharge, and diagnosis).

All data are coded. Participants are given a 1 digit site code, a 3 digit screening code, and if randomized a 2 letter + 3 digit randomization code. The VA crosswalk between participant identities and code number is kept electronically on the VA research drive. The list is only accessible to the personnel listed on the R&DC application. The Madigan crosswalk is kept electronically on a secured site only accessible to Madigan study personnel.

Original Source Documents and CRFs will be kept at each clinical site. Copies of CRFs will be kept at VA Puget Sound. Copies of CRFs from Madigan will either be shipped to VA Puget Sound via trackable method (i.e. Fed-Ex, UPS) or will be transported to VA Puget Sound by one of the study staff in HIPAA-compliant locked containers. CRFs will be stored in locked offices.

CRFs are kept in restricted access areas. Coded data (with no identifiers save study visit date) will be kept on shelves in areas that are locked at all times. Source documents (which contain identifiers) will be kept in file cabinets in locked areas. File cabinets are locked when the rooms are unoccupied. Electronic data will be kept on the VA research server. Access to the Electronic data will be restricted to persons listed on the Coordinating Center IRB application.

We are required by our funding agency to collect TBI Common Data Elements (CDEs). The National Institute of Neurological Disorders and Stroke (NINDS) and several co-sponsoring Federal agencies have the common mission of developing data standards for clinical research. Through the efforts of subject-specific working groups, the NINDS, along with several co-sponsoring Federal agencies developed the first set of CDEs in 2010. To broaden the utility of the TBI CDEs, experts were asked to update the recommendations to make them relevant to all ages, injury severity, and phases of recovery. The second version of the TBI CDEs (v.2) was developed in 2012.

We are required to transmit the CDEs to the Federal Interagency Traumatic Brain Injury Research (FITBIR) informatics system. FITBIR is a biomedical informatics system and data repository, created by the Department of Defense and the National Institutes of Health to assist biomedical researchers working to develop a better understanding of traumatic brain injury and/or to develop more effective methods to diagnose, treat and prevent traumatic brain injuries. Specific information about FITBIR code generation is described in section 9.0 below.

There is a risk of loss of confidentiality. We will be creating/updating medical records in the EHR. Because of this, all clinical labs will be ordered through the EHR systemand results will be placed automatically in it. We are not ordering any clinical labs which would contain sensitive information (i.e., are not performing drug, HIV, or hepatitis testing). When ordered through the EHR, pregnancy test results will be placed in the EHR.

We have obtained a Federal Certificate of Confidentiality to protect against compelled disclosure

of answers to the questionnaires. However, Certificates of Confidentiality do not apply to active duty SMs, due to requirements that information bearing on the SMs health may be required to be reported to appropriate medical or command authorities. In addition, disclosure of any illegal activities or sensitive information, such as drug use, is required to be reported to the SM's Commanding Officer, which may affect the participant's military career. These limits to SM's confidentiality are included in the Madigan consent form.

# 8.0 Communication Plan

The study Coordinating Center will be the MIRECC at VA Puget Sound. [name] is the PI of the overall study and of the Coordinating Center. All data management and analysis procedures will take place at VA Puget Sound. The Coordinating Center will also maintain records of all IRB and subcommittee submissions and approvals, and will coordinate communication between sites.

The VA Puget Sound study coordinator will be responsible for ensuring proper conduct of the clinical trial at VA Puget Sound and is a member of the Coordinating Center regulatory team. The Madigan Study Coordinator will have weekly contact with the VA Puget Sound Study Coordinator. The protocol and all amendments are prepared by Coordinating Center Personnel and e-mailed to the Madigan study coordinator for submission to the Madigan IRB. A template consent and HIPAA Authorization form will be given to the Madigan Study Coordinator who will then alter it per Madigan IRB requirements and submit it to the Madigan IRB. Similarly, any changes to the consent form will be e-mailed to the Madigan Study Coordinator by the VA Puget Sound Study Coordinator. All approvals from the Madigan IRB will be submitted to the VA Puget Sound IRB for their records.

The Coordinating Center staff at VA Puget Sound will maintain the IRB files from Madigan and all correspondence from the Army's Human Research Protection Office (HRPO). Because the VA Puget Sound Study Coordinator is a member of the Coordinating Center staff, which prepares all protocol amendments and consent form changes, he/she will be aware of any outstanding submissions and will ensure that all approvals are in place before the study begins and that they remain current during the duration of the study.

Reports of all SAEs, AEs, unexpected, but not serious AEs, unanticipated problems, and expected AEs will be shared between the VA and Madigan teams as they are reported. Detailed reporting criteria are described in section 6.0 above.

# 9.0 Information Security and Data Storage/Movement

The study Coordinating Center will be the MIRECC at VA Puget Sound. [name] is the PI of the overall study and of the Coordinating Center. All data management and analysis procedures will take place at VA Puget Sound. Coordinating Center Personnel will have access to protected health information. In addition, Study personnel as listed on the IRB applications at each site will have access to protected health information.

All data are coded. Participants are given 1digit site code, a 3 digit screening code, and if randomized a 2 letter + 3 digit randomization code The crosswalk between participant identities and code number are kept at each site. The VA site will store the crosswalk electronically on the VA research drive. The list is only accessible to the personnel listed on the R&DC application. The Madigan crosswalk will be stored confidentially, accessible only to personnel on the Madigan IRB application per Madigan DCI protocols and approved application. VA and Madigan Committees that oversee research (VA IRB, R&DC, Madigan Department of Clinical Investigation, Regional Health Command-Pacific IRB (Madigan) the Army Clinical Investigation Regulatory Office [CIRO])as well as the following regulatory bodies may have access to PHI, but will not be able to remove PHI from any facility: other Federal agencies including, but not limited to, the Food and Drug Administration (FDA), the Office for Human Research Protection (OHRP), the VA Office of Research Oversight (ORO), the VA Office of the Inspector General (OIG), Department of Defense (DOD), U.S. Army Medical Research and Materiel Command (USAMRMC) Office of Research Protections (ORP) Human Research Protection Office (HRPO), and the Government Accountability Office (GAO).

SIBCR will be provided with the full name, address, telephone numbers, and social security number of participants in order to authorize payment for participation in the study

**Physical Transportation of Identifying or Sensitive Data:** Because all data storage, entry, and analysis will take place at VA Puget Sound, copies of CRFs from Madigan subjects will be shipped via trackable method (Fed-Ex, UPS, etc.) or physically transported to VA Puget Sound by study staff in HIPAA-compliant locked containers.

There will be no physical transportation of data collected from participants at VA Puget Sound (only Madigan participants).

**Electronic Transmission of Data:** We are required by our funding agency to transmit research data and related findings to the FITBIR informatics system as described in section 7.0 above. FITBIR is a restricted access portal to search data relevant to TBI research. A FITBIR account is required to submit or access TBI-related data. Investigators and data managers at research sites are invited to request an account. To provide maximum protection for the confidentiality of research participants whose data is stored in FITBIR, professional credentials are verified by the FITBIR Data Access & Quality Committee (DAQ) during the account request process.

Data submitted to the FITBIR will be de-identified such that the identities of data subjects cannot be readily ascertained or otherwise associated with the data by the FITBIR staff or secondary data users. In addition, de-identified data will be coded using a unique code known as a GUID (Global Unique Identifier). Use of the GUID minimizes risks to study participants because it keeps one individual's information separate from that of another person without using names, addresses, or other identifying information. The unique code also allows FITBIR to link together all submitted information on a single participant, giving researchers access to information that may have been collected elsewhere. The GUID is a computer-generated alphanumeric code [example: TBI 1A462BS] that is unique to each research participant (i.e., each person's information in FITBIR—or each subject's record—has a different GUID). Creating the GUID involves several steps.

- The researcher uses his/her computer to enter pre-defined personal identifiers about research participants (e.g., birth name, date of birth) into a specific computer program provided by FITBIR. The program processes these personal identifiers at the researcher's site into several intermediary codes known as "hash codes." PII cannot be extracted from these hash codes; they are strictly one-way hash algorithms
- The hash codes are then sent from the researcher's institution to the GUID server at FITBIR where they are assigned a GUID. The GUID server also stores the hash code-to-GUID relationship to ensure that the same research participant consistently is assigned

the same GUID irrespective of whether he/she participates in different research studies or at different research sites.

- The GUID server returns the GUID to the researcher, who assigns it to the research participant's information.
- FITBIR cannot accept data without the GUID.

The GUID process has two important attributes: PII is never sent to the FITBIR system, and the GUID is a random number not generated from PII/PHI

**Clinical Trials.Gov:** A description of this clinical trial will be available on http://www.ClinicalTrials.gov, as required by U.S. law.

**Final Disposition of Data:** The link between study code and participant identity will be retained for six years after study closure, at which point it will be destroyed per guidelines in place at the time of destruction and all study data will become anonymous. Exceptions are if a participant agrees to specimen/data banking, the link will be retained indefinitely.

